8.1 Data collection and management

Patient's personal data will be collected (in anonymous form), date of birth, gender, weight, height, liver and hepatic enzymes, past clinical history, thrombotic/haemorrhagic risk factors, lifestyle habits, type of treatment, clinical events during the follow-up.

The monitor of the study will check data quality and completeness by remote monitoring.

Data will be anonymously entered by the investigator in the eCRF, by assigning a patient identification code.

The adopted database is MySQL and it will be produced by Softime90 Snc company.

Data anonymously entered in the eCRF will be recorded and stored in the server of the S. Orsola-Malpighi University Hospital in Bologna.

Each access to the eCRF will be managed by personal user name and a password.

The security system requires that the password be changed at the first access; it requires a length of at least 8 characters and provides for a periodic 3-month expiry.

It is obviously possible to disable the login, if it is deemed necessary by the system administrator.

Investigators can have full access only to their patient's data.

Every night the data backup is automatically performed.

The Study Monitor will send blind to the Safety Committee the data of the occurred events and all the necessary related information for their assessment.

8.2 Ethics

The study will be conducted in accordance with the ethical principles that have their origin in the Declaration of Helsinki and in compliance with the protocol and ICH-GCP.

This is an observational study and all drug prescriptions and clinical investigations are independent from the study.

Patients will receive the type and dosage of DOAC on the base of clinical characteristics at the discretion of the attending physician, as the normal clinical practice, independently from the decision to enrol the patient in the study.

The protocol and any amendments and the informed consent form (or information/non-opposition letter, as allowed by local regulations) will have to obtain Institutional Review Board or Ethics committee (IRB/EC) approval prior to initiation of the study.

8.3 Informed consent forms

Participation in this study is entirely voluntary. Informed consent will be obtained in accordance with the Declaration of Helsinki, ICH GCP and local regulations. A properly executed, written, informed consent will be obtained from each subject prior to entering the subject into the trial.

Information should be given in both oral and written form and subjects (or their legal representatives) must be given ample opportunity to inquire about details of the study. If appropriate and required by the local IRB/IEC, assent from the subject will also be obtained. If a subject is unable to sign the informed consent form (ICF) a legal representative may sign for the subject. A copy of the signed consent form will be given to the subject or legal representative of the subject and the original will be maintained with the subject's records.

Once a patient has been enrolled in the study, he/she may withdraw his/her consent to participate in the study at any time without prejudice. Patients will not be entered in the database if the informed consent has not been obtained.

8.4 Administrative issues

8.4.1 Support of the study

Participation in the MAS study is entirely voluntary and no form of remuneration or refund is given to the investigators.

The MAS study is supported by own funds of the Promoter, for the preparation, working and maintenance of all the necessary activities, i.e. informatic and monitoring activities, centralization, storage and distribution of plasma aliquots, reagents for laboratory activities, secretary needs, statistical analysis of results, production of reports and publication of scientific papers.

Fondazione Arianna Anticoagulazione will free provide to the Italian centres the material for plasma collection, buying the cryogenic storage tubes.

Becton Dickinson supports the study by the free supply of blood sampling tubes for Italian centres. The Promoter will also support the costs for the shipment of the material to Italian centres and for the centralization of Italian plasma samples and their further distribution to the centres chosen for the execution of laboratory tests.

9. Publication

9.1 Role of Promoter and Investigators

The Promoter and the investigators may suggest specific analysis, regarding all or some data of the central database. The authorship of the article must provide who proposed the analysis, who performed the data analysis, who took part in writing the article.

The role of the Promoter and investigators in the study (study design, collection, management, data analysis and interpretation, report writing, authorship) should be described.

9.2 Data handling and record keeping

All data and results and all intellectual property rights to the data and results derived from the study will be the property of the Promoter Fondazione Arianna Anticoagulazione according to D.M. 17 Dicembre 2004. This study is a No Profit Study (D.M. 17 Dicembre 2004, Art. 1, comma 2, lettera c)


APPENDIX 1

Labelling code

1. Alphanumeric code chosen by the centre
2. Date of collection
3. V (uppercase) for trough sample and P (lowercase) for peak sample

Example of labelling: "Alphanumeric code/01/01/2018/V", that identify the trough sample of a patient dated 01/01/2018.

That code has to be inserted in the proper field in the eCRF (tube code)

APPENDIX 2

OUTCOME DEFINITIONS

VENOUS THROMBOEMBOLISM (VTE)

Pulmonary embolism (PE)

Symptoms of PE with one of the following findings.

- A new intraluminal filling defect in (sub) segmental or more-proximal branches on spiral computed tomography (CT) of the chest.
- A new intraluminal filling defect, or an extension of an existing defect, or a new sudden cutoff of vessels more than 2.5 mm in diameter on the pulmonary angiogram.
- A new perfusion defect of at least 75% of a segment, with a local normal ventilation result (high probability) on ventilation/perfusion lung scintigraphy (VQ scan).
- Inconclusive spiral CT, pulmonary angiography, or VQ scan evidence of a new or recurrent PE, with demonstration of a new or recurrent deep vein thrombosis (DVT) in the lower extremities by compression ultrasound (CUS) or venography.

Proximal deep vein thrombosis (DVT)

Symptoms of DVT with one of the following findings.

(a) For a NEW DVT: abnormal CUS, or an intraluminal filling defect on venography.

(b) For a RECURRENT DVT:

- abnormal CUS where compression had been normal or, if non-compressible during screening, a substantial increase (4 mm or more) in diameter of the thrombus during full compression, or
- an extension of an intraluminal filling defect, or a new intraluminal filling defect, or an extension of non-visualization of veins in the presence of a sudden cut-off on venography.

DEATH

For all patients who died during the study, the cause of death was adjudicated to one of the following categories.

- VTE-related death
 - ✓ PE (based on objective diagnostic testing, autopsy)
 - ✓ Unexplained death (and VTE cannot be ruled out)
 - ✓ Sudden death (and VTE cannot be ruled out).
- Cardiovascular (CV)-related death
 - ✓ Myocardial infarction (MI)
 - ✓ Stroke
 - ✓ Other CV event (to be specified).
- Other
 - ✓ Cancer
 - ✓ Bleeding

- ✓ Infectious disease
- ✓ Other known cause (to be specified).

BLEEDING EVENTS

Major bleeding event

A major bleeding event was defined as a bleeding event (as per International Society on Thrombosis and Haemostasis guidelines ¹¹), as follows.

- Acute clinically overt bleeding accompanied by one or more of the following.
 - ✓ a decrease in hemoglobin of 2 g/dl or more
 - ✓ a transfusion of 2 or more units of packed red blood cells
 - ✓ bleeding that occurs in at least one of the following critical sites: intracranial, intraspinal, intraocular, pericardial, intra-articular, intramuscular with compartment syndrome, retroperitoneal
 - ✓ fatal bleeding

Clinically relevant non-major bleeding event

The definition of clinically relevant non-major bleeding was acute clinically overt bleeding that consists of:

- any bleeding compromising hemodynamics
- any bleeding leading to hospitalization
- subcutaneous hematoma larger than 25 cm², or 100 cm² if there was a traumatic cause
- intramuscular hematoma documented by ultrasonography
- epistaxis that lasted for more than 5 minutes, was repetitive (i.e. two or more episodes of bleeding more extensive than spots on a handkerchief within 24 hours), or led to an intervention (e.g. packing or electrocoagulation)
- gingival bleeding occurring spontaneously (i.e. unrelated to eating or tooth brushing) or lasting for more than 5 minutes
- hematuria that was macroscopic and was spontaneous or lasted for more than 24 hours after instrumentation (e.g. catheter placement or surgery) of the urogenital tract
- macroscopic gastrointestinal hemorrhage, including at least one episode of rectal blood loss, if more than a few spots on toilet paper
- hemoptysis, if more than a few speckles in the sputum and not occurring within the context of PE
- any other bleeding type considered to have clinical consequences for a patient such as medical intervention, the need for unscheduled contact (visit or telephone call) with a physician, or temporary cessation of a study drug, or associated with pain or impairment of activities of daily life

Minor bleeding events

All acute clinically overt bleeding events not meeting the criteria for either major bleeding or clinically relevant non-major bleeding were classified as minor bleeding.

Fatal bleeding event

A fatal bleeding event was defined as a bleeding event that the adjudication committee determined was the primary cause of death or contributed directly to death.

APPENDIX 3

Sample collection protocol

1. Select the patient treated with one of the direct acting oral anticoagulants, which you want to include in the study. Besides other characteristics (see protocol for further details) the patient must express (after appropriate information) the availability to perform a trough and a peak (optional) withdrawal, to be carried out preferably in the morning, just before taking the daily dose (or one of two daily doses, for double-dose drugs). Trough withdrawal should be performed 12 hours after the last dose of dabigatran or apixaban and 24 hours after the last intake of rivaroxaban or edoxaban.
2. For each sample it is required a total blood volume of 9-10 ml (e.g. 2 tubes of 4.5 ml or 4 tubes of 2.7 ml), taken with a vacuum system, containing citrate at the concentration of 0.109 M (3.2%).
3. Centrifuge (within 2 hours from sampling) for 15 minutes at 2,000xg at controlled room temperature (20°C).
4. Separate the plasma, without disturbing the cells, and mix it in a single plastic tube. Dispense the plasma into cryogenic storage tubes in aliquots of 0.5 mL, taking care to prepare as many as possible (with that blood volume - see above - the tubes will be at least 7-8). Each tube will be labelled by a code (see Appendix 1) that identifies centre, patient, date of collection and indicates whether it is a trough or peak sample.
5. Cap the tubes and move them into a freezer -70°C as soon as possible. If it is possible, it would be recommended to quickly freeze the plasma, before transfer it to the freezer, by immersion for a few seconds in liquid nitrogen or 10 minutes in an alcohol and dry-ice bath. If a freezer -70°C is not available, samples can be stored in a freezer -30°C for up to 3 months.
6. Move the samples to the Biobank of the Promoter, according to the planning and method indicated in the study protocol.

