3.3.2 Exclusion criteria

- age < 18 years
- indication for electrical cardioversion at the moment of drug prescription
- participation in Phase II or III clinical trials
- indication for treatment different from NVAf
- not suitable to give or not giving informed consent
- not available for blood collection or follow-up

4. Study procedures

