5.2 Outcomes during the follow-up

5.2.1 Primary outcomes

1. Bleeding complications (Appendix 2): a composite of:
 - Major bleeding (ISTH definition) (17)
 - Clinically relevant non-major bleeding (18)
2. Thromboembolic complications (Appendix 2):
 - objectively documented cerebral vascular event
 - systemic embolism with angiographic demonstration of abrupt arterial occlusion
3. Mortality (cardiovascular and total)

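### Appendix 2 files sudden and unexplained deaths under VTE-related death, so on the natural reading they drop out of cardiovascular mortality, a primary outcome

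*Combined protocol and SAP*

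**What the plan says.** Section 5.2.1 lists as its third primary outcome "Mortality (cardiovascular and total". It gives no definition of the cardiovascular part.

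The only cause-of-death scheme is in Appendix 2, under Death. It says that "the cause of death was adjudicated to one of the following categories" and gives three:

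- **VTE-related:** PE shown by objective testing or autopsy, "Unexplained death (and VTE cannot be ruled out", and "Sudden death (and VTE cannot be ruled out".
- **"Cardiovascular (CV)-related death":** myocardial infarction, stroke, and "Other CV event (to be specified".
- **Other:** cancer, bleeding, infectious disease, and "Other known cause (to be specified".

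The cohort is restricted to atrial fibrillation: section 3.3.2 excludes patients with an "indication for treatment different from NVAf".

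**The concern.** The scheme makes VTE the default for a death whose cause is not established, in a cohort where no one is treated for VTE. A sudden death is counted as cardiovascular only if VTE can be excluded. The protocol asks for no autopsy or imaging after death, so that may often be impossible.

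What is at stake is the cardiovascular part of a primary outcome. If sudden deaths leave the count, fewer events remain to relate to drug level, and the remaining mix leans towards infarction and stroke with a documented cause. The VTE-related category, meanwhile, mixes proven pulmonary emboli with deaths of undetermined cause.

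There is a second ambiguity in the same list. A fatal intracranial haemorrhage fits both Stroke (cardiovascular) and Bleeding (Other). In a study that relates anticoagulant level to outcome, that choice moves deaths plausibly linked to level into or out of cardiovascular mortality.

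**Working it through.** **Reading the text.** The plan gives no figure for this point, so there is none to reproduce.

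1. Each death has one category (Appendix 2), so a death placed under VTE-related cannot also be CV-related.
2. Sudden and unexplained deaths are named only under VTE-related, on condition that VTE cannot be ruled out.
3. The residual item under CV-related asks for a specified event, and the residual item under Other asks for a known cause. An undetermined death therefore fits nowhere except VTE-related.
4. No section adds VTE-related deaths back into cardiovascular mortality or defines it in another way.

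**Size.** The documents give no mortality rate and no cause shares, so every input here is an assumption. Documented PE deaths are left out of the arithmetic.

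- s = share of all deaths that are sudden or unexplained, 10-30%.
- c = share of all deaths that are otherwise cardiovascular, 30-50%.
- f = fraction of s that is truly cardiovascular.
- g = fraction of those truly cardiovascular deaths in which VTE cannot be ruled out.

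True cardiovascular share = c + sf. Share counted under the CV-related category alone = c + sf(1 − g). Hence:

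undercount = sfg / (sf + c)

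Upper bound, f = g = 1 (every such death is cardiovascular and VTE is never excluded):

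- s = 0.10, c = 0.50: 0.10/0.60 = 17%
- s = 0.20, c = 0.40: 0.20/0.60 = 33%
- s = 0.30, c = 0.30: 0.30/0.60 = 50%

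With f = g = 0.5:

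- s = 0.10, c = 0.50: 0.025/0.55 = 5%
- s = 0.20, c = 0.40: 0.05/0.50 = 10%
- s = 0.30, c = 0.30: 0.075/0.45 = 17%

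**The opposite error.** Suppose the VTE-related and CV-related categories are added together, and let h be the fraction of the non-cardiovascular sudden or unexplained deaths in which VTE cannot be ruled out. Then:

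overcount = s(1 − f)h / (sf + c)

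With f = h = 0.5 this is 0.025/0.55 = 5% to 0.075/0.45 = 17%, as large as the undercount at f = g = 0.5. If the other deaths are classified correctly, the true count lies between the count with undetermined deaths included and the count without them.

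**Absolute scale.** For 4000 patients (section 6.2), assume one-year mortality of 2-5% and 40-60% of deaths truly cardiovascular. That gives 4000 × 0.02 × 0.40 = 32 to 4000 × 0.05 × 0.60 = 120 cardiovascular deaths, or 8 to 30 per drug. Losing 10% leaves 29 to 108 overall; losing 50% leaves 16 to 60.

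**The case against.** The strongest reply is that the protocol never equates cardiovascular mortality with the CV-related category. If the sponsor means to pool VTE-related deaths into it, nothing is lost from this source, and unexplained deaths that are not cardiovascular would inflate the count instead. This stands in part. The undercount depends on a reading that the text invites but does not state. Under either reading a primary outcome lacks a usable definition.

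Second, the rule is conditional, and section 4.1 provides for an Adjudication Committee. The committee could exclude VTE on clinical grounds and record a sudden cardiac death as a specified other cardiovascular event. This also stands, and it is why g can be below 1.

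Third, on intracranial haemorrhage, Appendix 2 lists the intracranial site under major bleeding and defines fatal bleeding by the committee's judgement of its part in the death. Together these favour Bleeding. But Stroke is not defined and no order of precedence is given, so the overlap remains.

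A reader might also draw three stronger conclusions that the documents do not support:

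- *That most deaths filed as VTE-related would not be VTE.* No figure in the protocol bears on this.
- *That the study's mortality results as a whole are compromised.* Total mortality, and the section 5.2.2 composites that use it, do not depend on cause. The primary objective in section 2 and the sample size in section 6.2 rest on bleeding and thromboembolism.
- *That every sudden and unexplained death should simply be called cardiovascular.* That could overcount, as the working shows.

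**Conclusion.** The point holds in a limited form. Read naturally, the single-category rule in Appendix 2 takes sudden cardiac deaths out of cardiovascular mortality whenever VTE cannot be excluded, and nothing in the protocol puts them back. This is more than a missing detail, because a stated rule directs adjudicators to a category outside the one that the outcome appears to use.

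The size cannot be computed from the documents. The 17-50% range is a ceiling under the assumed shares and should not be quoted as the expected loss; 5-17% under the milder assumptions is equally illustrative. Both rest on cardiovascular mortality meaning the CV-related category alone. The consequence is confined to the cardiovascular part of one primary outcome. The change should be made, but the study's main question does not turn on it.

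**What to change.** 1. In section 5.2.1, state that cardiovascular mortality is the sum of the VTE-related and CV-related categories of Appendix 2.
2. In Appendix 2 and on the adjudication form, code sudden death and unexplained death as separate items, distinct from objectively documented PE.
3. In section 6.3, add a sensitivity analysis of cardiovascular mortality with the undetermined deaths excluded.
4. In Appendix 2, assign fatal intracranial haemorrhage to one named category.

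The cost is a few lines of text and a small change to the adjudication form, with no new data collection. The drawback is that some unexplained non-cardiovascular deaths may be counted as cardiovascular; the sensitivity analysis will show how far that matters. The change is best made before deaths are adjudicated, so that coding is consistent and the definition is not chosen after the results are seen.
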